### **Concomitant Medication Date Flag**

If not a complete date then

Y – If year of the imputed date is not equal to YYYY else M – If month of the imputed date is not equal to MON else D.

#### **5.1.3.1 Prior therapies date imputation**

Same as above.

#### **5.1.3.2 Post therapies date imputation**

Same as above.

### **5.1.4 Other imputations**

#### **5.1.4.1 Time**

If it is a start date or date/time of test done and date is not missing, then;

1. If seconds component is missing then seconds component is imputed as 00.
2. If minutes and seconds component is missing then minutes and seconds component are imputed as 00 and 00 respectively.
3. If whole time component is missing then Time component is imputed as 00:00:00.

If it is an end date and date is not missing, then;

1. If seconds component is missing then seconds component is imputed as 59.
2. If minutes and seconds component is missing then minutes and seconds component are imputed as 59 and 59 respectively.
3. If whole time component is missing then Time component is imputed as 23:59:59.

#### **5.1.4.2 Medical History**

For the calculation of duration or time since relevant history events in Section 2.3.3 (Baseline Characteristics), partial dates will be imputed for the MS diagnosis start date, the first MS symptom date, and the most recent relapse onset date via the below imputation rules.

- If the year is missing or impossible (e.g., 12-Jan-1911), then the date will be imputed as missing.

- If the year is not missing and possible, but the month is impossible or missing (e.g., 17-XXX-2010), then the year will be kept and date will be imputed as July 1st (e.g., 1-July-2010).
- If the year and the month are not missing and possible, but the day is impossible or missing (e.g., 31-Feb-2009), then the year and month will be kept, and date will be imputed as 15th (e.g., 15-Feb-2009).
- The imputed dates should be prior to the screening date. That is, if imputed dates are on or after the screening visit date, the dates will be imputed to be one day before the screening visit date.

When the onset date of most recent relapse is missing, then the date of diagnosis is considered as Onset Date of Most Recent Relapse.

## 5.2 AEs coding/grading

Adverse events will be coded using the Medical Dictionary for Regulatory Activities (MedDRA) terminology. The latest MedDRA version will be used and will be described in the footnote of relevant outputs.

AEs will be assessed according to the Common Terminology Criteria for Adverse Events (CTCAE). The CTCAE represents a comprehensive grading system for reporting the acute and late effects of cancer treatments. CTCAE grading is by definition a 5-point scale generally corresponding to mild, moderate, severe, life threatening, and death. This grading system inherently places a value on the importance of an event, although there is not necessarily proportionality among grades (a grade 2 is not necessarily twice as bad as a grade 1). The CTCAE grade of 5 (death) is not used; rather, 'fatal' is collected as AE outcome and death information is also collected on a separate eCRF page.

## 5.3 Laboratory parameters derivations

Laboratory results in the form AVAL = “< X”, where X is a positive number, and the numeric form is not available, will be derived as AVAL=AVALC/2. If it is a valid decimal number then AVAL will be numeric value of AVALC. If AVALC is in any other form, it will be kept as missing.

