#### **Multiple assessments**

It is possible that multiple assessments of a patient fall into the same visit-window (e.g., due to unscheduled visits). All results (scheduled and unscheduled) will be displayed in listings, but only one value (observed or derived) will be selected for summary statistics by visit-window.

For quantitative variables, the assessment closest to the target day will be selected. If more than one assessment is at the same distance to the target day, the later one will be selected.

For tables displaying the worst case scenario, such as shift tables or notable abnormalities, all assessments within a visit window will be used to identify the worst (e.g. the maximum or the minimum depending on parameter).

- **Baseline:** The last non-missing measurement made prior to or on the date of administration of the first dose of study treatment (the reference start date / Day 1). Only date part is considered if just one assessment on Day 1. If there are multiple assessments on Day 1, the following rules will apply:
  - a. If assessment time exists,
    - select the last available measurement prior to reference start date/time considering time;
  - b. If assessment time does not exist, select the available measurement from the lowest CRF visit number.
- **Post-baseline:** The measurement closest to the target day will be used. In the event two measurements are taken equally apart (e.g., 1 day before target date and 1 day after), the later one will be used. Cases where the same parameter is recorded more than once on the same date will be handled as follows:
  - a. If time of completion exists, the latest measurement will be used;
  - b. If time does not exist, the measurement from the lowest CRF visit number will be used.

In case categorical variables are based on continuous variables, the visit will be assigned to the continuous variable, and this visit will be used for the derived categorical variable.

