## **2.8.2 Laboratory data**

The summary of laboratory evaluations will be presented for three groups of laboratory tests: hematology, chemistry and urinalysis. Each group will be further subdivided into subgroups and presented as per [Table 5-1](#). Summary statistics for the change from baseline to each time point will be tabulated for each laboratory parameter. Data summaries will be provided in SI units.

In addition, shift tables based on normal ranges will be provided for all parameters in [Table 5-1](#) to compare participants' baseline laboratory evaluation relative to the visit's observed value and to the worst post-baseline value.

Number of participants with newly occurring liver enzyme abnormalities at any time post baseline will be summarized. Newly occurring liver enzyme abnormalities are defined in [Section 5.3.2](#).

All laboratory data will be listed by participant and visit/time point and if normal ranges are available, abnormalities will be flagged.

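### A laboratory result reported only as `>X` stays missing under SAP 5.3, so, if any occur, it cannot count as a high in tables built from AVAL

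*SAP*

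**What the plan says.** SAP section 5.3 turns the reported text (AVALC) into a number (AVAL) by three rules. A result of the form `<X`, "where X is a positive number, and the numeric form is not available, will be derived as AVAL=AVALC/2". For plain numbers, "If it is a valid decimal number then AVAL will be numeric value of AVALC". For the rest, "If AVALC is in any other form, it will be kept as missing". Neither the SAP nor the protocol has a separate rule for `>X`, so it falls under the third.

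These planned outputs depend on high laboratory values:

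- **Shift tables.** Under SAP 2.8.2, "shift tables based on normal ranges will be provided for all parameters" of Table 5-1, "to compare participants' baseline laboratory evaluation relative to the visit's observed value and to the worst post-baseline value". The SAP text on multiple assessments, under visit windows, says that for worst-case tables "all assessments within a visit window will be used to identify the worst (e.g. the maximum or the minimum depending on parameter".
- **Liver-enzyme abnormalities.** SAP 5.3.2 counts participants above multiples of the ULN, up to 20 times for ALT and AST. Its combined criteria require the elevations on the same sample day.
- **Change from baseline.** SAP 2.1.1.10 computes it only when both the baseline and the post-baseline value exist.

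The reported result is not removed from the record. SAP 2.8.2 adds: "All laboratory data will be listed by participant and visit/time point and if normal ranges are available, abnormalities will be flagged".

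**The concern.** The rule treats the two ends of the reporting range differently. A result too low to quantify stays in the summaries as an approximate number. A result too high to quantify has no number at all. For most chemistry parameters the high end is the one of safety interest, and such a result is at least as high as any the assay can express. If values go missing because they are high, the missingness carries information about severity, and a table that takes a maximum uses the next milder result. The study has a single arm, so no comparator column would reveal the loss.

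**Working it through.** The plan gives no figure to reproduce. The check applies the three rules literally and follows the result into the outputs.

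**Step 1: the derivation.** The example results are assumed; the rules are those of SAP 5.3.

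| Reported result | Rule that applies | AVAL |
|---|---|---|
| `<5` | halved: 5 / 2 | 2.5 |
| `12.3` | valid decimal | 12.3 |
| `>1000` | any other form | missing |

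Halving is written as AVALC/2, although AVALC holds the text `<X`; X/2 is evidently meant. `>=1000` and `<=5` also end as missing.

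**Step 2: worst post-baseline value.** Assume post-baseline results `25`, `>1000`, `38` and a ULN of 40.

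- Rule as written: max(25, 38) = 38, which is below 40, so the worst category is normal.
- With `>1000` taken as 1000: max(25, 1000, 38) = 1000, so the worst category is high.
- If `>1000` is the only post-baseline result, the participant has no worst value as written, and 1000 otherwise.

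**Step 3: liver thresholds.** Suppose these were ALT results. Then 1000 / 40 = 25, so `>1000` exceeds all of the 3, 5, 8, 10 and 20 times ULN thresholds in SAP 5.3.2. As written, the largest usable ratio is 38 / 40 = 0.95, and none is met. A combined criterion also fails if one component on that sample day has no number.

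**Step 4: change from baseline.** With no post-baseline AVAL at a visit, SAP 2.1.1.10 gives no change, and the participant leaves that summary.

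**Step 5: the baseline side.** The SAP takes the last non-missing value up to first dose as baseline. Protocol Table 8-1 schedules chemistry and hematology at both screening and Day 1. Suppose screening is normal, Day 1 is `>X` with X above the ULN, and a later result is above the ULN. As written, baseline falls back to the normal screening value and the later high becomes a normal-to-high shift. With `>X` retained, baseline is already high and nothing is new. Here the rule adds an apparent abnormality.

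**The case against.** The strongest reply is that the effect may never arise. No section gives an upper reporting limit or shows that the central laboratory returns `>X` for any test in Table 5-1. The halving rule applies only where no numeric form is available, so the paragraph can fairly be read as leaving any number supplied by the laboratory in place. The shift tables are described as based on normal ranges, and a laboratory high/low flag could supply the category without AVAL. All of this stands, and it is why the point is conditional. None of it supplies a rule for a `>X` result without a number.

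A reader might also infer more than the documents support:

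- **That the error always runs toward fewer abnormalities.** Step 5 shows the opposite can happen. Where the worst value is a minimum, losing a `>X` changes it only if no other value exists.
- **That every affected participant loses the high category.** Another result above the ULN preserves it. Protocol 8.4.5 calls for repeats of certain abnormal results, and 10.2.1 requires repeat liver tests, so a second high is plausible.
- **That notable-abnormality counts are affected.** The notable laboratory criteria in SAP 2.8.2.1 are low IgG and low IgM. Losing a `>X` cannot hide a low value.
- **That safety findings disappear.** Listings keep the result, and Protocol 10.1.1 makes clinically significant abnormal results adverse events, which are tabulated.

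**Conclusion.** The point holds as a conditional one. Followed literally, SAP 5.3 leaves a `>X` result with no numeric form out of the maximum in the shift tables, the liver-threshold counts and change from baseline. It rests on two assumptions that the documents neither confirm nor rule out: that the laboratory reports at least one such result, and that these tables are built from AVAL. The number of affected results is unknown and may be zero.

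If the assumptions hold, missingness depends on severity. Post-baseline highs can be understated, and a `>X` lost at baseline can make a later high look newly occurring. The reach is limited to descriptive laboratory summaries in a study without hypothesis testing; the primary endpoint is untouched. This is a minor correction, worth making because the rule is explicit and would be programmed as written.

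**What to change.** Add to SAP 5.3 that a result reported as `>X` with no numeric form:

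1. is set to AVAL = X for summaries;
2. is classed as high in shift tables when X is at or above the ULN;
3. counts toward a liver threshold when X is at or above that threshold;
4. keeps its original text in listings.

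Items 2 and 3 must be stated separately from item 1. The liver criteria are strict inequalities, so AVAL = X would miss a threshold exactly equal to X even though the true value exceeds it. Conversely, classing every `>X` as high without comparing X with the ULN could misclassify a result whose X lies below it. The same edit can say how `>=X` and `<=X` would be read, should the laboratory use them.

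The cost is a short addition to the SAP and a few programming lines. No new data are needed.

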### 5.3.1 Laboratory test groups and subgroups

Laboratory test groups and subgroups are tabulated in [Table 5-1](#).

**Table 5-1      Laboratory test groups and subgroups with SI units**

Order	Laboratory Group Subgroups	Tests (SI unit)
1	Hematology Red blood cells  White blood cell differential  B cells	Hematocrit (ratio) Hemoglobin (g/L) Platelets (10E9/L) Erythrocytes (Red cell count) (10E12/L)  Basophils (10E9/L) Eosinophils (10E9/L) Lymphocytes (10E9/L) Monocytes (10E9/L) Neutrophils (10E9/L) Basophils/Leukocytes (%) Eosinophils/Leukocytes (%) Lymphocytes/Leukocytes (%) Monocytes/Leukocytes (%) Neutrophils/Leukocytes (%) Leukocytes (White cell count)(10E9/L)  CD19+ B cell counts (10E6/L)
2	Chemistry Renal function  Liver function  Other enzymes  Lipids	Creatinine (umol/L) Blood urea nitrogen (mmol/L)  ALT (U/L) Albumin (g/L) Alkaline phosphatase (U/L) AST (U/L) Bilirubin (direct/conjugated) (umol/L) GGT (U/L) Total bilirubin (umol/L) Total protein (g/L)  Amylase (U/L)  Cholesterol HDL (mmol/L) Cholesterol LDL (mmol/L) Triglycerides (mmol/L) Total cholesterol (mmol/L)

Order	Laboratory Group Subgroups	Tests (SI unit)
	Other	Random glucose (mmol/L) C-reactive protein (CRP) (mg/L)
	Electrolytes/Metabolism	Bicarbonate (mmol/L) Calcium (mmol/L) Chloride (mmol/L) Magnesium (mmol/L) Phosphate (mmol/L) Potassium (mmol/L) Sodium (mmol/L)
	Immunoglobulin	Total IgG (g/L) Total IgM (g/L)
3	Urinalysis	Erythrocytes (Blood)  Specific gravity Specific gravity (Ratio) Albumin Protein pH Leukocytes (White blood count)
4	Immunophenotyping T cells	CD3+CD20+ T cell counts (10E6/L)

### 5.3.2.1 Definition of characteristics for liver event overview summary

Characteristics: Liver events are categorized based on ALT and ALP measurements using the closest lab assessment +/- 7 days from the onset of the liver event into the following characteristics ‘Hepatocellular’ (ALT > 2xULN or ALT/ULN:ALP/ULN > 5), ‘Cholestatic’ (ALP > 2xULN or ALT/ULN:ALP/ULN ≤ 2), ‘Mixed’ (ALT > 2xULN and ALP > ULN and 2 < ALT/ULN:ALP/ULN ≤ 5), ‘None’ (if none of the three above qualifies), and ‘Unknown’ (in case of a missing ALT or ALP values). Note that the categories are not mutually exclusive. The definition is consistent with Novartis safety guideline on hepatotoxicity.

## 5.4 Other derivations

### 5.4.1 The Columbia-Suicide Severity Rating Scale (C-SSRS)

The Columbia-Suicide Severity Rating Scale (C-SSRS) includes 11 levels considered as standard for classifying suicidal ideation and behavior events.

These include five levels of suicidal ideation, five levels of suicidal behavior, and the category self-injurious behavior, no suicidal intent.

These categories and levels are defined in [Table 5-2](#):

**Table 5-2 Suicidal ideation and behavior categories and definitions**

Category number	C-SSRS category	Definition
Suicidal ideation		
1	Wish to be dead	Patient has thoughts about a wish to be dead or not alive anymore or wish to fall asleep and not wake up.
2	Non-specific active suicidal thoughts	General nonspecific thoughts of wanting to end one's life or commit suicide (e.g., “I've thought about killing myself”) without general thoughts of ways to kill oneself/associated methods, intent, or plan during the assessment period.
3	Active suicidal ideation with any methods (not plan) without intent to act	Patient has thoughts of suicide and has thought of at least one method during the assessment period. This situation is different than a specific plan with time, place, or method details worked out (e.g., thought of method to kill self but not a specific plan). Includes person who would say, “I thought about taking an overdose but I never made a specific plan as to when, where, or how I would actually do it . . . and I would never go through with it.”
4	Active suicidal ideation with some intent to act, without specific plan	Active suicidal thoughts of killing oneself, and patient reports having some intent to act on such thoughts, as opposed to “I have the thoughts but I definitely will not do anything about them.”

5	Active suicidal ideation with specific plan and intent	Thoughts of killing oneself with details of plan fully or partially worked out and patient has some intent to carry it out (i.e., some degree of intent is implicit in the concept of plan).
Suicidal behavior		
6	Completed suicide	A self-injurious behavior that resulted in fatality and was associated with at least some intent to die as a result of the act. Evidence that the individual intended to kill him- or herself, at least to some degree, can be explicit or inferred from the behavior or circumstance.
7	Suicide attempt	A potentially self-injurious behavior, associated with at least some intent to die as a result of the act. Evidence that the individual intended to kill him- or herself, at least to some degree, can be explicit or inferred from the behavior or circumstance. A suicide attempt may or may not result in actual injury.
8	Interrupted suicide attempt	When the person is interrupted (by an outside circumstance) from starting a potentially self-injurious act (if not for that, actual attempt would have occurred).
9	Aborted suicide attempt	When person begins to take steps toward making a suicide attempt, but stops before actually engaging in any self-destructive behavior. Examples are similar to interrupted attempts, except that the individual stops before being stopped by something else.
10	Preparatory acts toward imminent suicidal behaviors	This category can include anything beyond a verbalization or thought, but it stops short of a suicide attempt, an interrupted suicide attempt, or an aborted suicide attempt. This might include behaviors related to assembling a specific method (e.g., buying pills, purchasing a gun) or preparing for one's death by suicide (e.g., giving things away, writing a suicide note).
Self-Injurious Behavior Without Suicidal Intent		
11	Self-injurious behavior associated with no intent to die. The behavior is intended purely for other reasons, either to relieve distress (often referred to as self-mutilation (e.g., superficial cuts or scratches, hitting or banging, or burns)) or to effect change in others or the environment.	

[figure not shown]
#### 5.4.2 TSQM-9 scoring

TSQM-9 scale scores range from 0 to 100 and no computed score should be lower or higher than these limits. If more than 1 item score is missing, the scale score should not be computed, and set to missing. The TSQM-9 scale scoring algorithm as described by [Atkinson et al.](#) is tabulated in [Table 5-3](#):

**Table 5-3 TSQM-9 scale scoring algorithm**

Domain	Scale score
--------	-------------

Effectiveness	$[(\text{Item 1} + \text{Item 2} + \text{Item 3} - 3) / 18] \times 100$ . If one item is missing then $[\text{sum}(\text{available items}) - 2 / 12] * 100$
Convenience	$[(\text{Item 4} + \text{Item 5} + \text{Item 6} - 3) / 18] \times 100$ . If one item is missing then $[\text{sum}(\text{available items}) - 2 / 12] * 100$
Global satisfaction	First recode create Item 9_R: $\text{Item 9\_R} = (\text{Item 9} - 1) \times 4 / 6 + 1$ Then the global satisfaction scale score is $[(\text{Item 7} + \text{Item 8} + \text{Item 9\_R} - 3) / 12] \times 100$ . If one item is missing then $[\text{sum}(\text{available items}) - 2 / 8] * 100$

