### **2.7.1 Secondary endpoints**

The secondary endpoints are as follows:

1. Retention on study treatment from baseline to Month 6, and to Month 12 (Yes, No)

2. Change from baseline in lymphocytes, including total CD19+ B cell counts and CD20+CD3+ T cell counts, obtained by fluorescence activated cell sorting (FACS) at Months 6 and 12
3. The Columbia Suicide Severity Rating Scale (C-SSRS) at Months 6 and 12
4. Treatment Satisfaction Questionnaire for Medication (TSQM-9) scores (including domains) at baseline vs Month 6 and vs Month 12
5. Treatment-emergent adverse events (TEAEs)

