### 2.11 Patient-reported outcomes

#### 2.11.1 Treatment Satisfaction Questionnaire for Medication-9 (TSQM-9)

The Treatment Satisfaction Questionnaire for Medication-9 (TSQM-9) is a 9-item general instrument that measures the major dimensions of satisfaction with a medication ([Bharmal et al. 2009](#)). Scores will be calculated for the effectiveness (Items 1-3), convenience (Items 4-6) and global satisfaction scale (Items 7-9). See [Appendix Section 5.4.2](#) for the scoring algorithm. Scores on the TSQM scale range from 0 (indicating poor satisfaction) to 100 (indicating perfect satisfaction).

Change from baseline in TSQM-9 scores for all 3 domains (effectiveness, convenience and global satisfaction) to Month 6 and 12 will be summarized for the FAS.

[REDACTED]

[REDACTED]

[REDACTED]

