## 5.5 Statistical models

### Primary analysis

Type is no hypothesis testing planned for this study.

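### The three one-item-missing TSQM-9 formulas in SAP Table 5-3 lack a bracket around the numerator, so as written they can only return scores above 100

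*SAP*

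**What the plan says.** SAP 5.4.2 sets the limits: "TSQM-9 scale scores range from 0 to 100 and no computed score should be lower or higher than these limits". It also says when no score is produced: "If more than 1 item score is missing, the scale score should not be computed, and set to missing". The special formulas in Table 5-3 therefore apply only when exactly one of a domain's three items is missing.

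For each domain, Table 5-3 gives a complete-data formula and then a fallback that begins "If one item is missing then". Write S for the sum of the items used.

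| Domain | All three items present | One item missing, as printed |
|---|---|---|
| Effectiveness, convenience | [(S − 3) / 18] × 100 | [S − 2 / 12] × 100 |
| Global satisfaction | [(S − 3) / 12] × 100, with Item 9_R in S | [S − 2 / 8] × 100 |

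The global satisfaction cell opens with the instruction "First recode create Item 9_R", defined as (Item 9 − 1) × 4/6 + 1. Its complete-data formula names Item 9_R. Its fallback refers only to the items available.

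The scores feed a secondary endpoint, listed in SAP 2.7.1 as "Treatment Satisfaction Questionnaire for Medication (TSQM-9) scores (including domains) at baseline vs Month 6 and vs Month 12". The analysis is descriptive: SAP 2.11.1 plans a summary, on the full analysis set, of how each of the three domains changes between baseline and those two visits.

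**The concern.** The complete-data formulas bracket the numerator and the fallback formulas do not. Under ordinary operator precedence the division is done first, so the fallback subtracts 2/12 or 2/8 from the item sum and multiplies the result by 100. The smallest possible sum of two items is 2, so such a score cannot come near the 0–100 scale. The table thus contradicts the limit stated directly above it.

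Table 5-3 is the only scoring rule in either document. A programmer who follows it meets the contradiction and has to choose a way out that the plan does not give: restore the bracket, truncate at 100, or set the score to missing. Truncation would turn every such response into perfect satisfaction. Setting to missing would go against the evident intention to score a domain with one absent item. A secondary endpoint's scoring rule should not leave that choice open.

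A smaller point sits alongside. The global satisfaction fallback does not say whether Item 9 enters the sum raw or recoded.

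**Working it through.** **Inputs.** The formulas and the 0–100 limit come from SAP 5.4.2 and Table 5-3. The SAP does not state the item response ranges; I infer them from its divisors.
- Items 1–6: 18 = 3 × 6, so each item spans 6 points, 1 to 7.
- Items 7, 8 and 9_R: 12 = 3 × 4, so each spans 4 points, 1 to 5.
- Item 9 raw: the recode maps 1 to 1 and 7 to (7 − 1) × 4/6 + 1 = 5, so the raw range is 1 to 7.

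**Step 1: complete-data formulas.** These reproduce the SAP's limits exactly.
- Effectiveness, convenience: S runs from 3 to 21, giving (3 − 3)/18 × 100 = 0 and (21 − 3)/18 × 100 = 100.
- Global satisfaction: S runs from 3 to 15, giving (3 − 3)/12 × 100 = 0 and (15 − 3)/12 × 100 = 100.

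**Step 2: one-item-missing formulas as printed.**
- Effectiveness, convenience: S runs from 2 to 14. Minimum (2 − 2/12) × 100 = 183.3; maximum (14 − 2/12) × 100 = 1383.3. None of the 7 × 7 = 49 response pairs falls within 0–100.
- Global satisfaction, using Item 9_R or with Item 9 itself missing: S runs from 2 to 10. Minimum (2 − 2/8) × 100 = 175; maximum (10 − 2/8) × 100 = 975. None falls within 0–100.

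**Step 3: the same formulas with the numerator bracketed.**
- Effectiveness, convenience: (2 − 2)/12 × 100 = 0 and (14 − 2)/12 × 100 = 100.
- Global satisfaction with Item 9_R: (2 − 2)/8 × 100 = 0 and (10 − 2)/8 × 100 = 100, whichever item is missing.

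The constants also fit. Dropping one item takes 3 to 2, 18 to 12 and 12 to 8, so the printed numbers are those of the bracketed form.

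**Step 4: examples for effectiveness.**

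| Sum of two items | As printed | Bracketed |
|---|---|---|
| 4 | (4 − 2/12) × 100 = 383.3 | (4 − 2)/12 × 100 = 16.7 |
| 10 | (10 − 2/12) × 100 = 983.3 | (10 − 2)/12 × 100 = 66.7 |

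**Step 5: Item 9, after the bracket is restored.** The question arises only if Item 7 or Item 8 is the missing one. If raw Item 9 were summed, the score would differ from the Item 9_R score by [Item 9 − Item 9_R] / 8 × 100 = (Item 9 − 1) / 24 × 100. That is 0 points at Item 9 = 1 and 25 points at Item 9 = 7. The maximum would be (5 + 7 − 2)/8 × 100 = 125. Of the 5 × 7 = 35 response pairs, three exceed 100: (4, 7), (5, 6) and (5, 7), with Item 7 or 8 first and Item 9 second. A range check would therefore miss most such errors.

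**The case against.** The strongest reply is that this is a self-evident slip. The intended formula can be read off the neighbouring one, the constants match it, and literal code would give values so far out of range that the SAP's own limit ("no computed score should be lower or higher than these limits") would expose them. The endpoint is one of five secondary endpoints and is only summarised, with no hypothesis testing in the study. All of that stands. It makes a silent error in the reported results unlikely, but it does not make the printed rule correct.

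A bracket lost when the table was converted to text cannot be ruled out. It is less likely than a slip in the source: the bracket is absent from all three fallback formulas, while those around the complete-data numerators in the same cells survive.

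Three stronger readings are tempting, and the documents do not support them.
- *That the secondary endpoint is mis-scored.* The fallback applies only with exactly one item missing in a domain, and nothing in the documents says how often that happens. The effect could be nil.
- *That change from baseline would be biased upwards.* This assumes truncation at 100, which the SAP does not prescribe; its limit reads as a validity condition. Even with truncation, TSQM-9 is also collected at baseline (protocol Table 8-1) and change is post-baseline minus baseline (SAP 2.1.1.10). A truncated baseline score would push the change downwards, so the net direction depends on which visits have the missing item.
- *That the SAP permits raw Item 9.* The recode is ordered first in the same cell and the score follows from it, so the available items are most naturally Items 7, 8 and 9_R. This is an ambiguity worth closing, not a stated error.

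**Conclusion.** The point holds as a formula error in the fallback scoring rule. As printed, all three one-item-missing formulas contradict the 0–100 limit for every possible response: 183.3 to 1383.3 for effectiveness and convenience, and 175 to 975 for global satisfaction with Item 9_R. These figures rest on normal operator precedence and on item ranges inferred from the SAP's divisors. The conclusion that nothing falls in range needs only that no item scores below 1.

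The reach is limited to domain scores with exactly one missing item. Complete questionnaires are scored correctly and the primary endpoint is untouched. Neither the size nor the direction of any effect on the summarised change from baseline can be derived from the documents.

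**What to change.** In SAP Table 5-3, replace the three fallback formulas:
- Effectiveness and convenience: [(sum of available items − 2) / 12] × 100.
- Global satisfaction: [(sum of available items − 2) / 8] × 100, adding that the items are 7, 8 and 9_R, and that raw Item 9 is never summed.

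Then confirm that the programmed derivation matches the corrected table, including a test record with Item 7 or 8 missing, because a range check alone would not catch most uses of raw Item 9. The cost is three formula corrections, one clarifying phrase and a short program check. No data collection or other analysis changes.
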